6.2.3 Follow up period and trial completion

Visit 8 - 2 days after the last study dose +3 days:

All assessments planned at this visit must be performed by all subjects after 48 hours of the last intake of study medication (+3 days), including those who have been prematurely withdrawn from the trial. Study medication should be completely tapered according to clinical practice at this visit except the patient who will continue the Pramipexole IR/SR treatment. Assessments performed during visit 8 include the following:

- Obtain vital signs (blood pressure, pulse) and weight
- Perform MMIDI interview
- Collect fasted blood sample for safety laboratory evaluation if abnormal at visit 7
- Perform 12-lead ECG if abnormal at visit 7

- Perform compliance check of taper medication
- Review concomitant therapies including PD therapies
- Record AEs or follow-up on AEs continuing from a prior visit

End of the trial is defined as the last visit (**follow up visit**) completed by each patient.

7. STATISTICAL METHODS AND DETERMINATION OF SAMPLE SIZE

Details of all analyses will be provided in the TSAP.

7.1 STATISTICAL DESIGN - MODEL

This is a two-stage multicentre, open-label, randomized, active controlled parallel group phase IV study. This two-stage study includes stage I and stage II. The stage I part of this trial will be conducted as a pilot study to explore the difference of change from baseline to week 18 in PDSS-2 total score between Pramipexole SR and IR. Stage II will be planned as a confirmatory or exploratory design. Stage I and II are totally separated, and the patients in Stage I will not be used in Stage II.

7.2 NULL AND ALTERNATIVE HYPOTHESES

For pilot stage I, there is no (confirmatory) hypothesis testing foreseen in a strict statistical sense. Analyses are descriptive in nature including two-sided p-values and confidence intervals throughout from statistical models used for explorative purposes.

For stage II, the assumption of the hypothesis testing will be based on the results of pilot stage I, which will be added once the topline results of stage I are worked out.

7.3 PLANNED ANALYSES

The analysis on the efficacy and safety endpoints will be based on the following populations:

- Treated set (TS) is defined as all patients who were dispensed study medication and were documented to have at least one dose of investigational treatment.
- Full analysis set (FAS) is defined as all patients who were randomized to treatment and received at least one dose of study drug and providing a baseline and at least one PDSS-2 total score measurement in maintenance period.
- Per protocol set (PPS) is defined as a subset of FAS, including only patients without important protocol violations for efficacy. Details will be provided in the TSAP.

The primary efficacy endpoint will be analyzed on the FAS (as the primary analysis) as well as on the PPS (as the sensitivity analysis). The secondary and further efficacy endpoints will be analyzed on the FAS.

Safety endpoints will be analyzed on the TS.

Demographic and baseline characteristics will be analyzed on the TS using descriptive statistics.

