Week(s)	-2 to -1	0	1	2	3	4	5	6	7	8	12	18	Not applicable
Day(s)	-14 to -3	0	7	14	21	28	35	42	49	56	84	126	Last study dose +2
Time window for visits Day(s)	0	0	±2	±2	±2	±2	±2	±2	±2	±3	±3	±3	+3
Written Informed consent ³	x												
Assign patient number	x												
Supply Trial identification card	x												
Demographics	x												
Medical history	x												
Review of In-/exclusion criteria	x	x											
Physical examination	x											x	
BP, Pulse, Weight, Height ⁴	x	x		x		x				x	x	x	x
Check for abnormal behavior ⁷				x		x					x		
MMIDI		x								x		x	x
MMSE	x												
Modified Hoehn and Yahr stage at on-time	x												
Randomization		x											
Instruct and supply patient diary	x												
Review patient diary		x											
EMO		x		x		x				x	x	x	

Proprietary confidential information © 2018 Boehringer Ingelheim International GmbH or one or more of its affiliated companies

Trial Period	S ¹	R ¹	Flexible up-titration phase							Maintenance phase			Follow up visit after <down titration phase/EOT>
Visit	V1	V2	TC1	V3	TC2	V4	TC3 ¹¹	TC4 ¹¹	TC5 ¹¹	V5	V6	V7 ²	V8 ²
Weeks	-2 to -1	0	1	2	3	4	5	6	7	8	12	18	Not applicable
Days	-14 to -3	0	7	14	21	28	35	42	49	56	84	126	Last study dose +2
Time window for visits Day(s)	0	0	±2	±2	±2	±2	±2	±2	±2	±3	±3	±3	+3
CGI-I						×				×		×	
PGI-I			×	×	×	×	×	×	×	×	×	×	
ESS		×		×		×				×	×	×	
PDSS-2		×		×		×				×	×	×	
NHQ		×		×		×				×	×	×	
SCOPA-Sleep		×		×		×				×	×	×	
PDQ-8		×								×		×	
Safety lab tests	×											×	×
Urine Pregnancy test ⁹ (if applicable)	×											×	
12-lead ECG	×											×	×
Dispense trial drugs		×		×		×				×	×	×	
Compliance check			×	×	×	×	×	×	×	×	×	×	×
Concomitant therapy	×	×	×	×	×	×	×	×	×	×	×	×	×
Adverse events	×	×	×	×	×	×	×	×	×	×	×	×	×
Instruct and supply health economics questionnaire	×	×		×		×				×	×		
Review health economics questionnaire ¹⁰		×		×		×				×	×	×	

1. Abbreviations are for “Screening” and “Randomization”.
 2. All assessments planned at visit 7 and visit 8 have to be done even if a patient is prematurely withdrawn from the treatment phase. For visit 8, follow up visit after down-titration phase or follow up visit after EOT (end of treatment) should be conducted after the end of residual effect period (i.e., 2 days after the last study dose)
 3. Re-consenting may become necessary when new relevant information becomes available and should be conducted according to the sponsor’s instructions.
 4. Height will only be measured at Screening (visit 1).

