6.2.2.2 Up-titration phase

Patients will have weekly contact to the study site during the up-titration phase either as office visits or telephone calls. The complete seven weeks of up-titration are used to safely increase the study medications to the highest tolerated optimal dose for effective response. The investigator should use his/her clinical judgment in adjusting the dose to a dose where clinical improvement is reached. Furthermore, if a patient is unable to tolerate an increased dose level, the medication can be lowered one level.

It is possible that the L-Dopa⁺ dose may need to be adjusted with the addition of Pramipexole (SR or IR) during the up-titration Phase.

Visit 3 (i.e., week 2) at day 14 ± 2:

- Obtain vital signs (blood pressure, pulse) and weight
 - Check for abnormal behavior. The MMIDI sub-scale has to be completed if the patient experiences any abnormal behavior
 - Ask patient to score the severity of EMO
 - Ask patient to complete the ESS
 - Ask patient to complete the PDSS-2
 - Ask patient to complete the NHQ Section 1. NHQ Section 2 should be completed by spouses or caregivers who are with the patients during the night at the same day. If no spouses or caregivers during the night, document it in the medical note and no need to complete NHQ Section 2.
 - Ask patient to complete the SCOPA-Sleep
 - Ask patient to complete the PGI-I questionnaire
 - Perform medication compliance check
 - Review concomitant therapies including PD therapies
 - Record AEs or follow-up on AEs continuing from a prior visit
 - Dispense study medication to the patient to ensure the sufficient study medication until the next on-site visit with verbal instructions on how to take the medication. Remind the patient to take the study medication Pramipexole IR regularly three times per day with the third dose at 7-9 pm before bedtime or take study medication Pramipexole SR once daily at 7- 9 pm before bedtime. Additionally, remind the patient to bring the medication boxes (including all blank blister(s), unused and partially used study medication) back at the next scheduled on-site visit. The unused and partially used study medication will be returned to patients for treatment after drug accountability until the end of treatment.
-
- Schedule patient's next contact (telephone call, TC2) to study site one week later

Visit 4 (i.e., week 4) at day 28 ± 2:

- Obtain vital signs (blood pressure, pulse) and weight

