6.2.2.3 Maintenance phase

In this phase three on-site visits will be performed (V5 to V7). During the maintenance phase, no dose adjustments will be allowed for the study medication. A patient's dose will be adjusted for medical reasons if considered in the best interest of the patient upon agreement between investigators and Sponsor.

Visit 5 - week 8, day 56 ± 3:

- Obtain vital signs (blood pressure, pulse) and weight
- Perform CGI-I questionnaire
- Ask patient to score the severity of EMO
- Ask patient to complete the PGI-I questionnaire
- Ask patient to complete the ESS
- Ask patient to complete the PDSS-2
- Ask patient to complete the NHQ Section 1. NHQ Section 2 should be completed by spouses or caregivers who are with the patients during the night at the same day. If no spouses or caregivers during the night, document it in the medical note and no need to complete NHQ Section 2.
- Ask patient to complete the SCOPA-Sleep
- Ask patient to complete the quality of life assessment (PDQ-8 and EQ-5D-5L)
- Perform medication compliance check
- Review concomitant therapies including PD therapies
- Record AEs or follow-up on AEs continuing from a prior visit
- Dispense study medication to the patient to ensure the sufficient study medication until the next on-site visit with verbal instructions on how to take the medication. Remind the patient to take the study medication Pramipexole IR regularly three times per day with the third dose at 7-9 pm before bedtime or take study medication Pramipexole SR once daily at 7- 9 pm before bedtime. Additionally, remind the patient to bring the medication boxes (including all blank blister(s), unused and partially used study medication) back at the next scheduled on-site visit. The unused and partially used study medication will be returned to patients for treatment after drug accountability until the end of treatment.

- Schedule patient's next visit (Visit 6) four weeks later

Visit 6 - week 12, day 84 ± 3:

- Obtain vital signs (blood pressure, pulse) and weight
- Check for abnormal behavior. The MMIDI sub-scale has to be completed if the patient experiences any abnormal behavior.
- Ask patient to score the severity of EMO
- Ask the patient to complete the PGI-I questionnaire
- Ask patient to complete the ESS questionnaire
- Ask patient to complete the PDSS-2

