- Ask patient to complete the NHQ Section 1. NHQ Section 2 should be completed by spouses or caregivers who are with the patients during the night at the same day. If no spouses or caregivers during the night, document it in the medical note and no need to complete NHQ Section 2.
- Ask patient to complete the SCOPA-Sleep
- Perform medication compliance check
- Review concomitant therapies including PD therapies
- Record AEs or follow-up on AEs continuing from a prior visit
- Dispense study medication to the patient to ensure the sufficient study medication until the next on-site visit with verbal instructions on how to take the medication. Remind the patient to take the study medication Pramipexole IR regularly three times per day with the third dose at 7-9 pm before bedtime or take study medication Pramipexole SR once daily at 7- 9 pm before bedtime. Additionally, remind the patient to bring the medication boxes (including all blank blister(s), unused and partially used study medication) back at the next scheduled on-site visit. The unused and partially used study medication will be returned to patients for treatment after drug accountability until the end of treatment.

- Schedule patient's next visit (Visit 7) six weeks later

Visit 7 - week 18, day 126 ± 3 or premature discontinuation:

All patients should complete these assessments, even those who terminate early.

- Obtain vital signs (blood pressure, pulse) and weight
- Perform comprehensive physical examination (including heart, lungs, abdomen, extremities, height and weight, etc.) including also a skin examination

- Perform CGI-I questionnaire
- Perform MMIDI

- Ask patient to score the severity of EMO
- Ask the patient to complete the PGI-I questionnaire
- Ask patient to complete the ESS questionnaire
- Ask patient to complete the PDSS-2
- Ask patient to complete the NHQ Section 1. NHQ Section 2 should be completed by spouses or caregivers who are with the patients during the night at the same day. If no spouses or caregivers during the night, document it in the medical note and no need to complete NHQ Section 2.
- Ask patient to complete the SCOPA-Sleep
- Ask patient to complete the quality of life assessment (PDQ-8 and EQ-5D-5L)

- Collect fasted blood sample for safety laboratory evaluation
- Perform spot urine pregnancy test (for females with childbearing potential)
- Perform medication compliance check
- Review concomitant therapies including PD therapies

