7.3.1 Primary endpoint analyses

Mean changes from baseline will be analyzed using a restricted maximum likelihood (REML) - based repeated measures approach. Analyses will include the fixed, categorical effects of treatment, visit in the maintenance period, and treatment-by-visit interaction, as well as the continuous, fixed covariates of baseline and baseline-by-visit interaction. An unstructured covariance structure will be used to model the within-patient measurements.

If this analysis fails to converge, the following covariance structures will be tested in order: (UN → ANTE (1) → SP (1)). The first model to converge will be used as the primary analysis. The Kenward-Roger approximation will be used to estimate denominator degrees of freedom. Descriptive p-values will be based on least-squares means using a two-sided $\alpha = 0.05$ (two-sided 95% confidence intervals). In case the model failed to converge under PROC MIXED, the “singular” option could be considered. The primary treatment comparisons will be the contrast between treatments at the endpoint visit.

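### The full analysis set and the primary model take maintenance-visit PDSS-2 only, so treated patients who leave during titration drop out of the primary analysis although weeks 2 and 4 are measured (minor)

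*Protocol*

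**What the plan says.** - **Analysis set.** Protocol 7.3 defines the FAS as randomised patients who took at least one dose, "providing a baseline and at least one PDSS-2 total score measurement in maintenance period". The primary analysis is run on this set. The per-protocol set is named for the sensitivity analysis: "Per protocol set (PPS) is defined as a subset of FAS".
- **Model.** Protocol 7.3.1: "Analyses will include the fixed, categorical effects of treatment, visit in the maintenance period, and treatment-by-visit interaction", with baseline and baseline-by-visit as covariates, an unstructured covariance, and the treatment contrast at the endpoint visit as primary. Section 7.3.2 applies the same method to the continuous secondary endpoints.
- **Which visits these are.** Protocol 6.2.2.3: "In this phase three on-site visits will be performed (V5 to V7"), that is weeks 8, 12 and 18.
- **What else is measured.** The flow chart and section 6.2.2.2 also schedule the PDSS-2 at Visits 3 and 4, weeks 2 and 4: "Ask patient to complete the PDSS-2".
- **Missing data.** Section 7.5 includes each patient to the extent that data exist, imputes nothing, and relies on a likelihood method under missing at random.
- **Early leavers.** They are asked for the Visit 7 assessments when they stop. Flow chart, footnote 2: "All assessments planned at visit 7 and visit 8 have to be done even if a patient is prematurely withdrawn". Section 6.2.2.3: "All patients should complete these assessments, even those who terminate early".

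**The concern.** A patient who stops during titration has a baseline, has taken study drug and may well have a week-2 or week-4 PDSS-2, yet has no maintenance-period score. The FAS rule removes that patient because of something that happens after randomisation.

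The model reinforces the rule. With maintenance visits as the only outcomes, such a patient contributes nothing to the likelihood. Missing at random is then conditional on treatment, baseline and maintenance scores only, so leaving in titration must be unrelated to the later score given treatment and baseline. If patients leave because their early scores are poor, weeks 2 and 4 are the data that would make the assumption credible, and they are outside the model. This also sits badly with section 7.5.

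The per-protocol analysis starts from the same set, so comparing it with the primary result says nothing about the excluded patients.

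At stake is the week-18 adjusted mean difference, which Table 3.3:1 compares with -3.44 when deciding on Stage II. Titration fills 7 of the 18 weeks, section 1.2 says adverse reactions mostly begin early, and the trial is open-label with a patient-rated endpoint. Early leaving could therefore differ by arm.

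**Working it through.** **Inputs from the protocol:** SD 8, N = 80, 86 randomised and 5% drop-out (7.7); 43 per arm (synopsis); cut-off -3.44 (Table 3.3:1); discontinuation for adverse reactions in the 18-week advanced-disease trial, 8/164 = 4.9% on SR and 8/175 = 4.6% on IR (1.2).

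**Assumed:** between-visit correlation 0.6 (range 0.4 to 0.8, equal for all visit pairs); baseline slope -0.4; 2 of 43 patients (4.7%) lost from one arm.

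**1. The plan's own figures.** SE = 8 × √(4/80) = 1.789. The probability of an observed difference at or below -3.44 is Φ((-3.44 − true difference)/SE):

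- true -4.00: Φ(0.56/1.789) = 62.3%
- true -5.00: Φ(1.56/1.789) = 80.8%
- true -3.00: Φ(-0.44/1.789) = 40.3%

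All 30 cells of Table 7.7:1 reproduce.

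**2. How many patients.** 0.05 × 86 = 4.3. If every drop-out fell in titration, the FAS would hold about 82. Section 1.2 also reports about 12% discontinuation on IR in older trials; at that rate, again all in titration, 0.12 × 86 = 10.3 would be lost. The shifts below use the plan's 5%.

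**3. Moderate selection.** One arm loses 5%, and the odds of leaving multiply by a fixed ratio per SD of week-4 score (2 million draws, correlation 0.6). Odds ratios of 1, 2 and 3 shift the week-18 contrast by 0.00, -0.16 and -0.24 points. In SE units, 0.16/1.789 = 0.09 and 0.24/1.789 = 0.13. A negative sign favours the arm with the losses.

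**4. Extreme and null cases.** 2000 simulated trials per case, 43 per arm, five visits; model with treatment-by-visit, baseline-by-visit and unstructured covariance; each trial compared with its own complete data; Monte Carlo SE at most 0.008. Shift of the week-18 contrast:

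| Who leaves | Correlation | Weeks 8, 12, 18 | Weeks 2, 4, 8, 12, 18 |
|---|---|---|---|
| One arm, 2 worst at week 4 | 0.4 | -0.29 | 0.00 |
| same | 0.6 | -0.44 | -0.01 |
| same | 0.8 | -0.58 | 0.00 |
| One arm, 2 worst on the unobserved week-8 score | 0.4 | -0.29 | -0.13 |
| same | 0.6 | -0.43 | -0.11 |
| same | 0.8 | -0.59 | -0.07 |
| One arm, 2 worst, before week 2, no score | 0.6 | -0.43 | -0.43 |
| Both arms, 2 worst each | 0.6 | +0.01 | +0.01 |
| One arm, 2 at random | 0.6 | +0.01 | 0.00 |

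The extreme of 0.44 is 0.44/1.789 = 0.25 SE.

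**5. Effect on the cut-off.** Take a true difference of -3.00 and put the losses in SR. The chance of reaching -3.44 rises from 40.3% to Φ((-3.44+3.16)/1.789) = 43.8% for a shift of 0.16, to Φ((-3.44+3.24)/1.789) = 45.5% for 0.24, and to 50.0% for 0.44.

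**6. Size of the covariance.** Three visits: 3 × 4/2 = 6 parameters. Five visits: 5 × 6/2 = 15.

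**The case against.** **The restriction has a rationale.** Weeks 2 and 4 fall in flexible titration, and the last titration decision is at week 7. That justifies reporting week 18. It is a weaker reason to leave the early visits out of the model: with treatment-by-visit and baseline-by-visit terms, early scores are not averaged into the week-18 contrast and act only through their correlation with later scores.

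**The stakes are limited.** This stands. Stage I is descriptive (7.2), its patients are not reused in Stage II (7.1), Table 3.3:1 is offered as guidance, and Scenarios B and C weigh other factors. The head-to-head discontinuation rates in section 1.2 are nearly equal. The 0.44 case requires all the loss in one arm and both leavers to be that arm's worst.

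**The benefit is partly built in.** This also stands. The fall from 0.44 to 0.01 occurs because simulated leaving depends on the very score then added, and equal correlation makes week 4 as informative about week 18 as week 12 is.

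**Stronger readings a reader might infer.**

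- Because Visit 7 is headed "Visit 7 - week 18, day 126 ± 3 or premature discontinuation", a titration leaver's score might be thought to enter as week 18. The protocol states no such rule. The heading governs data collection, and mapping discontinuation visits is ordinary SAP content.
- The early scores might be called unused. They lie outside the FAS rule, the primary model and the continuous secondary analyses that copy it; nothing bars other use, and the SAP may add sensitivity analyses.
- Unequal loss might be thought hidden. It would be visible, since baseline and safety use the treated set (7.3) and withdrawal reasons are reported (3.4.4.1).

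**Conclusion.** The point holds as a minor fault in wording that the protocol itself fixes. A SAP can settle visit windows, but bringing weeks 2 and 4 into the primary analysis would depart from sections 7.3 and 7.3.1.

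The likely shift is 0 to 0.24 points, at most 0.13 SE. The one-arm extreme is 0.44 points (0.29 to 0.58 across correlations 0.4 to 0.8), a quarter of an SE at 0.6. These sizes rest on the plan's SD of 8 and on the assumed correlation, baseline slope, 5% loss and one-sided loss. With similar losses in both arms the shift is about zero. The point is worth correcting because the remedy needs no new data, not because the Stage I result is in danger.

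**What to change.** - **Section 7.3:** define the FAS as randomised, treated patients with a baseline and at least one post-baseline PDSS-2.
- **Section 7.3.1 and the synopsis:** fit the same model to weeks 2, 4, 8, 12 and 18, with the week-18 contrast still primary. Both changes are needed together: widening the set alone adds patients who have no outcome in the model.
- **Sensitivity:** keep the present maintenance-only set and model.
- **Discontinuation scores:** when making the change, place them by actual study day.

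**Cost.** The work is wording only. The unstructured covariance has more parameters to estimate from about 80 patients; the fallback structures already listed in 7.3.1 apply if it does not converge. Nothing is gained for patients who leave before week 2 without a score, and the correction is only partial if leaving depends on scores never observed.

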7.3.1 Primary endpoint analyses

Mean changes from baseline will be analyzed using a restricted maximum likelihood (REML) - based repeated measures approach. Analyses will include the fixed, categorical effects of treatment, visit in the maintenance period, and treatment-by-visit interaction, as well as the continuous, fixed covariates of baseline and baseline-by-visit interaction. An unstructured covariance structure will be used to model the within-patient measurements.

If this analysis fails to converge, the following covariance structures will be tested in order: (UN → ANTE (1) → SP (1)). The first model to converge will be used as the primary analysis. The Kenward-Roger approximation will be used to estimate denominator degrees of freedom. Descriptive p-values will be based on least-squares means using a two-sided $\alpha = 0.05$ (two-sided 95% confidence intervals). In case the model failed to converge under PROC MIXED, the “singular” option could be considered. The primary treatment comparisons will be the contrast between treatments at the endpoint visit.

